### 6.4 Duration of Therapy

In the absence of treatment delays due to adverse event(s), treatment may continue for a total of 17 cycles or until one of the following criteria applies:

- Disease progression per RECIST v1.1
- Intercurrent illness that prevents further administration of treatment
- Unacceptable adverse event(s)
- Patient decides to withdraw from the study
- General or specific changes in the patient's condition render the patient unacceptable for

further treatment in the judgment of the investigator

- Clinical progression
- Patient non-compliance
- Pregnancy
  - All women of child bearing potential should be instructed to contact the investigator immediately if they suspect they might be pregnant (e.g., missed or late menstrual period) at any time during study participation.
  - The investigator must immediately notify CTEP in the event of a confirmed pregnancy in a patient participating in the study.
- Termination of the study by sponsor
- The drug manufacturer can no longer provide the study agent

The reason(s) for protocol therapy discontinuation, the reason(s) for study removal, and the corresponding dates must be documented in the Case Report Form (CRF).

## **6.5 Duration of Follow-Up**

Patients will be followed for up to 5 years from registration or until death, whichever occurs first. Patients will be seen in clinic 30 days after their last study treatment. Patients that discontinue study treatment for reasons other than disease progression will follow the imaging schedule – every 6 weeks in the first year, every 3 months in year 2, and then every 6 months until 5 years from registration. Patients who discontinue study treatment for disease progression will be followed every 3 months for the first 2 years from registration and then every 6 months until 5 years from registration. Follow-up assessment for survival may be done by telephone or email (preferred) if patients are no longer seeing the doctor in clinic.

## 7. DOSING DELAYS/DOSE MODIFICATIONS

A window of  $\pm 2$  days during induction is allowed for all in-clinic treatment days to account for holidays, inclement weather, and other unexpected conflicts. A window of  $\pm 3$  days for day 1 of each cycle is allowed during the maintenance phase.

### 7.1 Carboplatin and Etoposide

The following hematologic parameters must be met on **Day 1** of Cycles 1-4:

- Absolute neutrophil count (ANC)  $\geq 1500/\text{mm}^3$
- Hemoglobin  $\geq 8.0 \text{ g/dL}$
- Platelets  $\geq 100/\text{mm}^3$

If Day 1 parameters are not met and carboplatin and etoposide are held, all Day 1 treatments (carboplatin, etoposide, atezolizumab, and entinostat) will be delayed until parameters are met.

If delays  $>3$  weeks are required before carboplatin and etoposide can be resumed, induction will be discontinued. The patient may then initiate the maintenance regimen. Alternatively, the patient may discontinue all study treatment and standard of care atezolizumab may be continued per investigator discretion.

Supportive therapy with granulocyte colony stimulating factor (GCSF) in order to achieve Day 1 treatment parameters may be used per ASCO or NCCN guidelines.

Dose modifications for carboplatin and etoposide should be conducted per investigator discretion based on institutional standards and guidance from package inserts for each drug. In general, when dose modifications to entinostat are required (e.g., for hematologic adverse events), dose reductions for carboplatin and etoposide should strongly be considered unless the adverse event is clearly attributable to entinostat alone.

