### 7.2.3 Management and Dose Modifications for Entinostat

If carboplatin and etoposide are held during induction, entinostat and atezolizumab will also be held.

If at any time atezolizumab is held for atezolizumab-related AEs, instruct the patient to continue to take entinostat and to notify the study team if the event gets worse. If the adverse event worsens, entinostat should then be held with atezolizumab until the adverse event improves as specified in the below management and dose modification tables for both drugs. Entinostat may also be held at the investigator discretion for severe or life-threatening events.

If entinostat is held in either induction or maintenance regimen, the other study drug(s) will also be held, unless the adverse event can clearly be attributed only to entinostat and not to the other study drugs, in which case carboplatin, etoposide, and atezolizumab may be given in accordance with the regimen at the time (i.e. induction or maintenance).

The following specific management and dose modifications will be made for adverse events thought to be at least possibly related to entinostat. Patients requiring a delay of  $> 3$  weeks will discontinue entinostat. Patients that require a dose reduction when already receiving dose level - 1 (2 mg PO, weekly, as per table above) will discontinue entinostat. It is recommended that investigators maximize treatment for nausea, vomiting and diarrhea. No specific entinostat dose reductions are required for anemia.

Neutropenia	Management/Next Dose for Entinostat
≤ Grade 1	No change in dose
Grade 2	Hold* until ≤ Grade 1. Resume at same dose level.
Grade 3	Hold until ≤ Grade 1. Resume at one dose level lower **
Grade 4	Discontinue entinostat ***
* For grade 2 neutropenia events occurring mid-cycle, treatment does not need to be held ** For grade 3 neutropenia events occurring mid-cycle, treatment should be held, but dose reduction not required upon resuming. If event persists to day 1 of next cycle, resuming at one dose level lower is required. *** Entinostat should be held for grade 4 events occurring mid-cycle and may resume at one dose level lower with GCSF support upon recovery to ≤ Grade 1.	
For neutropenia events occurring between days 2 and 21 of each cycle that improve by day 1 of subsequent cycle, dose reductions may be made at investigator discretion. GCSF support should be considered on subsequent cycles.	

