Thrombocytopenia	Management/Next Dose for Entinostat
≤ Grade 1	No change in dose
Grade 2	Hold* until ≤ Grade 1. Resume at same dose level.
Grade 3	Hold until ≤ Grade 1. Resume at one dose level lower
Grade 4	Discontinue entinostat
* For grade 2 thrombocytopenia events occurring mid-cycle, treatment does not need to be held For thrombocytopenia events occurring between days 2 and 21 of each cycle, dose reductions at next cycle Day 1 may be made at investigator discretion, unless required as above	

Other non-hematologic AEs	Management/Next Dose for Entinostat
≤ Grade 2	No change in dose
Grade 3	Hold until ≤ grade 1. Resume at one dose level lower.
Grade 4	Discontinue entinostat

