## 9. STATISTICAL CONSIDERATIONS

### 9.1 Study Design/Endpoints

This is a phase 1 trial to evaluate the safety and efficacy of various doses of entinostat combined with atezolizumab, carboplatin, and etoposide therapy for patients with treatment naïve ES-SCLC. Four dose levels of entinostat are detailed in Figure 1. The Bayesian optimal interval (BOIN) design will be used to find the maximum tolerated dose (MTD) based on safety (Liu and Yuan, 2015; Yuan et al., 2016). The target toxicity rate for the MTD is 20%. Due to overlapping hematologic toxicities between chemotherapy and entinostat, it may be difficult to separate attributions specifically to entinostat, particularly for thrombocytopenia events. Our DLT definitions will count these more extreme hematologic events at DLTs, although it is recognized that these occur in the setting of carboplatin and etoposide chemotherapy alone. Therefore, it is anticipated that a 20% DLT rate is a conservative estimate of the true DLTs directly related to entinostat. Furthermore, small cell lung cancer is an aggressive malignancy with poor overall survival. Additional toxicity is justified if there is potential for efficacy gains. Dose-limiting toxicities (DLT) will be determined by adverse events occurring during the first cycle of treatment. DLTs are defined in Section 6.2.

The primary endpoints of the study are:

- MTD of entinostat
- Grade 3/4 adverse event rate as defined by CTCAE v5.0
- Number of cycles received of the combination of entinostat, atezolizumab, carboplatin, and etoposide (maximum = 4)

The secondary endpoint of the study is:

- 9-month PFS rate, defined as the proportion of patients alive and without disease progression after 9 months from study enrollment

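### The Day 1 platelet threshold in Section 7.1 is printed as 100/mm³, 1,000-fold below the entry value, and the entinostat hold rules only partly cover the gap

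*Combined protocol and SAP*

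**What the plan says.** Section 7.1 sets three conditions for Day 1 of Cycles 1 to 4: "Absolute neutrophil count (ANC) $\geq 1500/\text{mm}^3", haemoglobin of at least 8.0 g/dL, and "Platelets $\geq 100/\text{mm}^3". If they are not met and chemotherapy is held, all four drugs wait until they are. The section gives no other platelet figure: "Dose modifications for carboplatin and etoposide should be conducted per investigator discretion based on institutional standards" and on package inserts. It adds that chemotherapy reductions should be strongly considered when entinostat is modified.

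Section 3.1.10 requires, at entry, neutrophils of at least 1,500/mcL, haemoglobin of at least 9.0 g/dL and platelets of at least 100,000/mcL.

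Section 7.2.3 has its own thrombocytopenia table for entinostat. The Grade 2 entry is "Hold* until ≤ Grade 1. Resume at same dose level", with an exception for mid-cycle events. Grade 3 means a hold and a lower dose; Grade 4 means stopping entinostat. When entinostat is held, "the other study drug(s) will also be held, unless the adverse event can clearly be attributed only to entinostat". The tables are introduced with this scope: "The following specific management and dose modifications will be made for adverse events thought to be at least possibly related to entinostat".

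**The concern.** A platelet count of 100/mm³ is not a meaningful limit for giving carboplatin and etoposide. Read literally, nearly any patient satisfies it, so the protocol's only numeric platelet condition for chemotherapy does nothing. Sections 2.4.2.2 and 9.1 both name overlapping haematologic toxicity as a particular worry with this combination, so this condition should be the reliable one.

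The main stake is patient safety: a patient could receive Day 1 chemotherapy at a dangerous count and still be within the written protocol. The same list decides when a delayed cycle may restart. For patients still on entinostat whose low platelets are not attributed to it, the line can also bear on a primary endpoint, "Number of cycles received of the combination of entinostat, atezolizumab, carboplatin, and etoposide (maximum = 4").

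**Working it through.** **1. The ratio.** 1 mm³ = 1 mcL, so the two sections compare directly.

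| Parameter | Entry (3.1.10) | Day 1 (7.1) | Entry ÷ Day 1 |
|---|---|---|---|
| Neutrophils | 1,500/mcL | 1,500/mm³ | 1.0 |
| Haemoglobin | 9.0 g/dL | 8.0 g/dL | 1.125 |
| Platelets | 100,000/mcL | 100/mm³ | 1,000 |

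Only the platelet line is off by orders of magnitude. An implied multiplier of 1,000 for the whole list would make the neutrophil line absurd.

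**2. What passes the printed threshold.** The protocol grades by CTCAE v5.0 but prints no cut-offs. Assume lower limits of about 75,000, 50,000 and 25,000/mm³ for Grades 1, 2 and 3. The printed value is then 750, 500 and 250 times below them. All Grade 1 to 3 counts and nearly all Grade 4 counts would pass.

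**3. What Section 7.2.3 covers.** For a patient taking entinostat with at least possibly related thrombocytopenia, Day 1 Grade 2 or 3 holds entinostat and normally the other drugs. Three groups fall outside this:

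- *Level -1 induction.* The Section 6.1 schedule gives no entinostat in Cycles 1 to 4, so there is none to hold.
- *Entinostat already stopped.* The rule for a patient who needs a reduction at the lowest dose ends "2 mg PO, weekly, as per table above) will discontinue entinostat". Level 1, the starting level, is already 2 mg, so the first required reduction removes the backstop (Section 7.2.1).
- *Events not attributed to entinostat.* These are outside the stated scope of the tables.

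Two finer points. At Grade 4 the instruction is to stop entinostat, whereas the rule that carries the other drugs along is worded for a hold. At Grade 1 there is no dose change, so if Grade 1 reaches below 100,000/mm³ (the assumption in step 2), Section 7.2.3 does not replace a 100,000/mm³ condition even for patients on entinostat.

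**4. How many Day 1 checks are involved.** Cycle 1 is left out because the entry criterion largely covers it. Average patients at Level -1 = average trial size × percentage treated there (Section 9.1.3); multiply by 3 for Cycles 2 to 4.

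| Scenario | Average size | % at Level -1 | Patients | Checks |
|---|---|---|---|---|
| 1 | 23.7 | 5.6 | 1.3 | 4.0 |
| 2 | 23.7 | 10.6 | 2.5 | 7.5 |
| 3 | 22.3 | 25.7 | 5.7 | 17.2 |
| 4 | 19.4 | 41.3 | 8.0 | 24.0 |

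Across all levels there are at most 3 × 19.4 = 58.2 to 3 × 23.7 = 71.1 checks at the simulated average sizes, and 3 × 36 = 108 at the maximum size. These figures assume every patient reaches Cycle 4. The sizes of the second and third groups cannot be derived from the documents.

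**5. What is unaffected.** The Cycle 1 thrombocytopenia DLTs in Section 6.2 are defined by grade and bleeding, not by the Section 7.1 list. The escalation boundaries and the maximum of 36 do not use it either.

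**The case against.** The strongest reply is that this is a typing error whose intended value can be read from Section 3.1.10, and that any oncologist would read it as 100,000. A threshold is also a necessary condition, not an order to treat: counts are scheduled on Day 1 of every induction cycle, and institutional standards and package inserts still apply. Section 7.1 further urges chemotherapy reductions when entinostat is modified for haematologic events. These points lower the likely harm. None of them supplies a platelet number.

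The third uncovered group should be uncommon. At least possibly related is a low bar, Section 10.1.1.1 lists decreased platelets as a likely effect of entinostat, and Section 9.1 says attribution is hard to separate for thrombocytopenia. That is fair, and Level -1 and patients off entinostat are the firmer gaps. The second group is also narrower than any low count, because Day 1 Grade 2 resumes at the same dose.

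The check counts measure opportunity, not events; no rate of low Day 1 platelets is available, and 8.0 patients at Level -1 comes from the most toxic scenario simulated. The endpoint effect has no known size or direction, and a delay ends induction only beyond 3 weeks. Both limits stand.

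A multiplier lost from the platelet line alone when the text was extracted cannot be fully excluded. The neighbouring neutrophil line, in the same unit, came through as a full count.

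**Conclusion.** The concern holds. The platelet condition in Section 7.1 is wrong as written by a factor of 1,000, and it is an operative rule for giving cytotoxic drugs. The 1,000-fold figure rests only on the two printed values and the unit identity. Section 7.2.3 is a partial backstop: it leaves Level -1 induction, patients off entinostat and unattributed events without a working numeric platelet threshold for chemotherapy. The exposure at Level -1, about 4 to 24 checks per trial, is an upper figure that depends on the simulated scenarios and on full completion of induction. The consequence is mainly for safety; an effect on the count of combination cycles is possible but cannot be sized.

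**What to change.** Change the platelet line in Section 7.1 to at least 100,000/mm³, after the sponsor confirms that the entry value is meant to apply on Day 1. Confirmation is needed because haemoglobin differs between the two sections (8.0 against 9.0 g/dL), so the Day 1 values need not all equal the entry values. Use one unit in Sections 3.1.10 and 7.1, and notify sites so that order sets and dosing checks carry the corrected number.

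The cost is a one-line amendment and a site notice. Design, sample size and data collection stay as they are.

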## 7.2 Entinostat

### 7.2.1 Dose reductions for entinostat during induction

Dose Level 1	
Dose Reduction	Entinostat Dose
Starting Dose Level	2 mg, PO weekly
1 st Dose Reduction	Discontinue entinostat
PO = Orally	

Dose Level 2	
Dose Reduction	Entinostat Dose
Starting Dose Level	3 mg, PO weekly
1 st Dose Reduction	2 mg, PO weekly
2 nd Dose Reduction	Discontinue entinostat
PO = Orally	

Dose Level 3	
Dose Reduction	Entinostat Dose
Starting Dose Level	5 mg, PO weekly
1 st Dose Reduction	3 mg, PO weekly
2 nd Dose Reduction	2 mg, PO weekly
3 rd Dose Reduction	Discontinue entinostat
PO = Orally	

### 7.2.2 Dose reductions for entinostat during maintenance

Regardless of dose level assignment at the start of the trial, 5 mg PO weekly will be the starting dose in the maintenance phase for all patients who did not require entinostat dose reductions

during induction. If entinostat is reduced or discontinued during the induction phase of the trial due to hematologic adverse events, entinostat will be resumed at the maintenance dose of 5 mg PO weekly as long as the adverse event(s) that led to discontinuation of entinostat have improved to grade  $\leq 1$ ; otherwise resume at the same dose as the end of the induction phase. If entinostat was reduced due to non-hematologic adverse events during induction, it will be continued at the same dose level in maintenance. If entinostat was discontinued due to non-hematologic adverse events in the induction phase, it will not be restarted in the maintenance phase.

Dose Level	Entinostat Dose
Starting Dose Level*	5 mg, PO weekly
1 st Dose Reduction	3 mg, PO weekly
2 nd Dose Reduction	2 mg, PO weekly
3 rd Dose Reduction	Discontinue entinostat
* Starting dose level of entinostat for maintenance cycles is 5 mg, PO weekly, irrespective of assigned dose level during induction cycles. PO = orally	

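### For related neutropenia or thrombocytopenia still above Grade 1 when maintenance starts, Section 7.2.2 says to resume entinostat and Section 7.2.3 says to hold or discontinue it; for a patient already off entinostat, 7.2.2 names no dose

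*Combined protocol and SAP*

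**What the plan says.** Three parts of the combined protocol and SAP bear on the point, and a fourth sets the route into maintenance.

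- **Section 7.2.2 (maintenance).** The restart rule opens with "If entinostat is reduced or discontinued during the induction phase of the trial due to hematologic adverse events". Entinostat then goes to 5 mg weekly "as long as the adverse event(s) that led to discontinuation of entinostat have improved to grade" 1 or lower; "otherwise resume at the same dose as the end of the induction phase". For the other class of events the section is explicit: "If entinostat was discontinued due to non-hematologic adverse events in the induction phase, it will not be restarted in the maintenance phase".
- **Section 7.2.3 (management).** Its scope is stated as follows: "The following specific management and dose modifications will be made for adverse events thought to be at least possibly related to entinostat". It refers to holds in both induction and maintenance. For neutropenia and thrombocytopenia, Grade 2 is held until Grade 1 or lower and resumed at the same dose. The Grade 3 entry is "Hold until ≤ Grade 1. Resume at one dose level lower". Grade 4 means discontinuation. Patients who need a delay of more than 3 "weeks will discontinue entinostat".
- **Section 7.2.1 (induction reductions).** The last step at Dose Levels 1, 2 and 3 is "Discontinue entinostat". At Level 1, the starting level, this is the first reduction.
- **Section 7.1 (chemotherapy).** If carboplatin and etoposide would have to be delayed by more than 3 weeks, induction ends and the patient may go on to the maintenance regimen. The Day 1 blood count requirements are stated for Cycles 1 to 4 only.

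**The concern.** The alternative branch in 7.2.2 is reached only when the event has not come down to Grade 1 or lower, yet its instruction is to resume. Section 7.2.3 tells the site to hold or stop in that situation. Two sites could each follow the protocol text and treat the same unresolved cytopenia in opposite ways. For a patient whose entinostat was stopped in induction, the branch also points to a dose that does not exist.

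The first stake is patient safety. The second is the quality of the late safety data. Section 9.1.1 allows the recommended phase 2 dose to be set below the MTD after review of DLT-like events in later cycles and of discontinuations attributed to entinostat. Section 6.2 allows a cohort to be closed on events outside the DLT window. The Grade 3/4 adverse event rate, a primary endpoint in 9.1, is given without a time window, so maintenance events may count towards it. All of these are harder to interpret if maintenance entinostat was restarted under different rules.

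**Working it through.** No arithmetic applies and the plan states no figure on this point. The check compares each branch of the 7.2.2 rule with the 7.2.3 tables on the first day of maintenance, for neutropenia or thrombocytopenia at least possibly related to entinostat.

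| Status in induction | Grade at start of maintenance | 7.2.2 | 7.2.3 | Result |
|---|---|---|---|---|
| Reduced | 1 or lower | 5 mg weekly | No hold | No hold conflict |
| Reduced | 2 or 3 | Resume at end-of-induction dose | Hold until 1 or lower | Conflict |
| Reduced | 4 | Resume at end-of-induction dose | Discontinue | Conflict |
| Discontinued | 1 or lower | 5 mg weekly | No hold | Dose is defined |
| Discontinued | 2 or worse | Resume at end-of-induction dose | Hold or discontinue | No such dose exists; conflict if any positive dose is read in |

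**Do the exceptions in 7.2.3 remove the conflict?** No. The only exemption from holding is for Grade 2 events occurring mid-cycle, and maintenance begins on Day 1 of a cycle. For mid-cycle Grade 3 neutropenia the footnote relaxes the dose reduction, not the hold. For mid-cycle Grade 4 neutropenia, resumption depends on recovery to Grade 1 or lower. Grade 4 thrombocytopenia has no resumption footnote.

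**What if the 7.2.3 hold is applied first?** Entinostat then restarts only at Grade 1 or lower, where the first branch of 7.2.2 already assigns 5 mg. The second branch never operates for these two events. So for them the clause either contradicts 7.2.3 or has no effect.

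**Can the branch be reached?** Yes. Under 7.1 a patient whose chemotherapy would be delayed by more than 3 weeks may move to maintenance, and nothing in 7.1 requires counts to have recovered first. If the Day 1 counts were the cause, entinostat has been delayed as well, because 7.1 delays all Day 1 drugs together. For a related event, 7.2.3 then says a delay of more than 3 weeks means discontinuing entinostat. An event arising in Cycle 4 can also be unresolved at Cycle 5 Day 1, where no count requirement is stated.

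**Who can meet the undefined case?** A patient at any of the three levels that give entinostat in induction, since each reduction ladder ends in discontinuation and Grade 4 events or long delays can lead there directly. Level -1 gives no entinostat in induction, so it has nothing to reduce or discontinue.

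**A related gap.** The rule covers both reduced and discontinued entinostat, but its recovery condition names only events that led to discontinuation. Read literally, it does not state the condition for patients who were only reduced.

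**The case against.** The strongest defence reads the sections together: 7.2.3 decides when to hold and 7.2.2 decides the dose, so a site holds first and then looks up the dose. For a patient already off drug, the end-of-induction dose can be read as none, meaning the patient stays off. The group is also small. A patient who stopped entinostat early but continued chemotherapy had to meet the 7.1 counts before each later induction cycle, and one who recovered to Grade 1 or lower has a stated dose. Regular adverse event review (6.2) and calls at least monthly with the CTEP Medical Officer (13.1) offer a way to settle single cases.

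Part of this stands. The clause keeps a function for anaemia, which has no hold table, and for cytopenias not attributed to entinostat; there is no conflict in either case. The 7.1 counts do narrow the group. But for related neutropenia and thrombocytopenia the joint reading leaves the clause with nothing to do. If it is stretched to mean hold and then resume at the end-of-induction dose, which the text does not say, three doses compete on recovery: 5 mg, the end-of-induction dose, and one level lower after Grade 3. The stay-off reading is not written either: the text says to resume, while the same section spells out no restart for non-haematologic discontinuation. Case-by-case review does not give sites a common rule in advance.

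A reader might also infer more than the documents support:

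- *That 27.5% to 43.7% of patients are affected.* Those figures in 9.1.3 are the simulated shares treated at Level 1 (27.5, 37.7, 43.7 and 42.0 across the four scenarios). They are not rates of haematologic discontinuation, still less of events unresolved at maintenance.
- *That every haematologic reduction at Level 1 meets the problem.* Only unresolved events reach the second branch, and mid-cycle Grade 3 neutropenia need not force a reduction.
- *That the MTD is compromised.* Dose finding uses Cycle 1 DLTs, and the feasibility endpoint counts induction cycles, with a maximum of 4.
- *That 7.2.1 is also in conflict.* It is only the induction ladder and contradicts nothing.

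**Conclusion.** The point holds within limits. For neutropenia or thrombocytopenia at least possibly related to entinostat and still Grade 2 or worse when maintenance begins, 7.2.2 and 7.2.3 give incompatible instructions. Where entinostat had already been discontinued in induction for such an event, 7.2.2 gives no usable instruction.

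Its size cannot be stated. Being affected requires a haematologic reduction or discontinuation in induction, an event unresolved at the start of maintenance, and entry to maintenance, and the documents give no rate for any of these. The effect on the recommended phase 2 dose is indirect, since 9.1.1 says only that late safety data may lower it.

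The conclusion rests on two readings of the text: that the alternative branch means failure to improve to Grade 1 or lower, the only condition given, and that 7.2.3 applies in maintenance, as its reference to both regimens indicates. The contradiction is worth correcting before sites have to act on it, because one of the two literal readings leads to dosing during an unresolved cytopenia.

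**What to change.** The sponsor should reconcile 7.2.2 with 7.2.3, and with the route into maintenance in 7.1, so that the protocol states:

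1. one rule for a haematologic event that has not improved to Grade 1 or lower when maintenance begins, saying whether it differs for events not attributed to entinostat and for anaemia;
2. one rule for entinostat discontinued during induction for a haematologic event, covering patients who have recovered and those who have not;
3. a recovery condition in 7.2.2 that names reduction as well as discontinuation, to match the group the rule covers.

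Which dose or rule is right is a clinical decision for the sponsor, and none is proposed here. Section 7.2.1 needs no change on this account. The cost is a wording amendment, with no effect on sample size, visit schedule or the dose-finding design.
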